12.2. Sampling

Trial

Children will be recruited from primary care where the vast majority of children are managed. Selection bias will be minimised by encouraging recruiting sites to invite consecutive eligible patients and measured by asking them to record the characteristics of patients/reasons where this is not possible. Children not eligible for the trial or whose parents decline participation in the RCT will be invited to participate in the OCS.

Previous studies suggest 80-90% of children with AOM use antibiotics. The primary outcome of the study is to reduce antibiotic use in this group to 60-70%. Assuming 90% power and alpha set at 0.05 between 109 and 121 children would be needed in each of the active ear-drop and no-drop groups to detect a 20% reduction. As a key secondary outcome we are also interested in measuring whether the active eardrops reduce pain compared to the non-active ear-drops. Again using 90% power and alpha set at 0.05 a difference of 1.0 on the pain numerical rating scale (using an SD of 2.5 from our previous RCT suggests we need 133 children in each of the active and placebo ear drop groups. Thus using this slightly larger number of 133 children for all three groups and assuming no more than 20% attrition, we need to recruit 167 children per arm of the trial or 501 children in total.

A decision will taken as to whether children recruited during the initial 2 arm pilot (for the first 3 months, prior to the introduction of the delayed placebo) can be included in the analysis of the full 3 arm trial, following a review and comparison of the data collected under the two different randomisation schedules.

Observational cohort study

The observational study will have the similar, but slightly broader inclusion criteria and will be straightforward for patients who do not wish to participate in the trial because it will not involve any intervention. Participation in the observational study will simply involve completion of baseline and follow-up data collection instruments. For children whose parents do not wish them to be in the observational study, we will ask clinicians to record anonymous characteristics (gender, date of birth) and reasons for non-participation where possible. All site communications will emphasise the importance of recruiting to the trial over the observational study and sites will be limited to a trial:observational study recruitment ratio of 1:1 (this is higher than the ratio observed in one of our previous trials of antibiotics for adult chest infections in which the same ratio was approximately 2/3:1/3).

Qualitative study

Purposive sampling will attempt to capture maximum variation in views and experiences in order that they adequately reflect those of a range of parents with children with newly diagnosed AOM and health care professionals involved in their care. All parents agreeing to participate in the trial will be asked, at the time of consent, if they are willing to be contacted about taking part in a qualitative telephone_interview (see CEDAR participant and data flow diagram). From willing participants, a purposive sample will be drawn in relation to: (i) trial Centre (Bristol, Southampton, Cardiff); (ii) trial arm (active, placebo or no drop); and (iii) socio-demographic factors including child's age, ethnicity and socio-economic status (with participants being selected from areas of high and low social-economic deprivation, based on Index of Multiple Deprivation score).⁵⁰ In addition, telephone interviews will be conducted with a sample of parents that declined trial participation. Health care professionals (GPs, NPs, and ED doctors and nurses) involved in the trial will be purposively sampled in relation to: (i) trial Centre; (ii) type of primary care site (GP practice; Walk-in and Out of Hours Centres; Emergency Departments); and (iii) length of time since qualification. Sample sizes will be determined by the need to achieve data saturation, such that no new themes are emerging from the data by the end of data collection.⁴⁵ Interviews will be analysed in batches, and sampling will continue until no new themes are emerging. This is likely to include up to 25 health care professional and 30 parent interviews and 20 telephone interviews for those that declined trial participation or withdrew from the trial.

12.3. Randomisation

Blinding of participants

The participants will be blinded to the trial in that only one third will be aware that they are in the usual care group. We will present this arm of the trial to parents as "one of the three treatment paths within the trial to which children will be randomised", rather than as "the control arm".

During the initial 2 arm pilot period, parents and clinicians will be aware that treatment allocation is either to the active treatment arm (active ear drops and usual care) or to the usual care/no ear drops ("control") arm.

Blinding of recruiting clinicians

The randomisation process will ensure that that there is no opportunity for clinicians to influence which child is allocated to which treatment. Clinicians recruiting children to the trial will be blinded until after treatment allocation. Once written informed consent has been obtained, the parent will be given a Patient Pack which will be identical across all three arms. Once the pack is opened during the consultation, the clinician and parent will learn whether or not the child has been allocated to one of the ear drop arms – but will remain blinded to allocation between the active and placebo drops.

For children recruited within the initial 2 arm pilot period, allocation to the active treatment arm (active ear drops and usual care) or to the "control" arm (usual care/no drops) will be known by the clinician and parent at the point of recruitment, following the eligibility assessment and informed consent processes.

Stratification

We will stratify by centre so that the distribution of the three arms are fairly equal between Bristol, Cardiff and Southampton. We will use sites' proven record of recruitment to previous studies to inform the distribution of recruitment packs at start-up.

Block size

We will randomise in batches of 30 within which treatment allocation will be equal (10:10:10) (for the initial 2 arm pilot, treatment allocation will also be equal (10:10)). We will closely monitor the recruitment at each centre, and adjust the ratio of the number of blocks provided to primary care sites within each trial centre to ensure they receive patient and medicine packs in proportion to their rate of recruitment.

12.4. Minimising bias

Participants in clinical trials frequently differ from the general population with the condition of interest, and it can be a challenge to determine the degree and likely effects of any selection bias. In addition to trying to minimise selection bias by encouraging practices to recruit sequential eligible children and making the trial relatively straightforward to take part in, we will seek to measure selection bias, model the effects of any selection bias, and provide data on the presentation, management and outcomes of children with AOM who are not recruited into a trial, by conducting the observational study of children who are not recruited into the trial.

12.5. Statistical analysis

Quantitative analysis

The analysis and presentation of the trial will be in accordance with the CONSORT guidelines and a full analysis plan developed. Descriptive statistics will be used to assess balance in the randomised arms at baseline and will be presented as means and standard deviations for normally distributed variables, medians and inter-quartile ranges for any skewed variables, or numbers and percentages.

The first part of the primary comparison will be the prevalence of antibiotic use at Day 8 post consultation (where Day 1 is the day of randomisation) between those children receiving active eardrops and those receiving no drops (usual care) and will be analysed on an intention to treat basis. The time between consultation and antibiotic consumption will also be explored. Logistic regression will be utilised and the findings adjusted for marked imbalance at baseline (e.g. that differ by more than 0.5 standard deviations for age or univariable significant differences in proportions such as those with bilateral AOM). Post randomisation health care related variables such as other analgesics taken by the child (we will record the timing of the last dose of oral analgesics given to the child that day, prior to the daily parent-rated child ear pain score) will not be adjusted for in the main model but will be mediated for in a secondary analysis. For any continuous outcomes that are clearly non-normally distributed, appropriate transformations will be documented and justified in the model. To assess the potential effects of missing data, multiple imputation methods will be utilised in a sensitivity analysis.

The key secondary analysis will analyse the difference in pain scores, between the active and placebo groups, 24-36 hours after administration of drops. This information will be collected using the Symptom and Recovery Questionnaire by asking the parents to score their child's ear pain over the past 24 hours on the evening of Day 2. The analysis–will be conducted using linear regression, adjusting for baseline pain score (collected prior to randomisation) and centre. This will be followed by a linear regression model where all other principles described for the primary analysis above will be applied, including the potential mediating effect of antibiotic use and other analgesics on how this might affect the interpretation of the results. Other secondary analyses will use the appropriate regression method, and, as these will be exploratory in nature, the p-value will be presented but will interpreted with due caution. The analysis will be conducted using the statistical package STATA. The trial statistician and senior statistician will be blinded to the different arms of the trial for the main analysis.

At the pre-funding stage, two reviewers identified that the use of antibiotics and analgesics could influence the effect of the ear drops on pain. Although evidence suggests the effects of antibiotics are modest [[name] BMJ 2001], on consideration we agree and will not adjust for post-randomisation health care variables such as analgesics and antibiotics in our main models or when reporting our main results. However as part of secondary sensitivity analyses, we will look at the mediating effect of analgesics and antibiotics to help interpret and contextualise our main findings, with the potential for confounding kept in mind.

We will measure selection bias, model the effects of any selection bias, and provide descriptive data regarding the presentation, management and outcome of children with AOM who are not recruited into a trial. We found evidence that fewer than 44% of eligible children were recruited into AOM trials [Bains 2001] and that the most likely reason for not recruiting was severity. To test this within CEDAR and to inform the assessment of generalisability, we will compare the global illness severity scores, made by parents and clinicians at baseline, across the RCT and OCS.

A full Statistical Analysis Plan will be developed and reviewed by the Trial Steering Committee.

Health economic analysis

The economic analysis will consist of a cost-effectiveness analysis and cost consequence study. As antimicrobial resistance is such an important concern, we propose a cost-effectiveness analysis with antibiotic use as a proxy for this outcome as our primary economic analysis. The cost-consequence study (including quality of life) is a secondary economic analysis.

The primary economic analysis will take a societal perspective including costs to the NHS and the family. Our sample size calculations are based on the primary outcomes (antibiotic use and ear pain). Avoidance of antibiotic prescriptions is a key economic outcome because of the large intangible costs of antibiotic resistance.⁵⁶ The economic case for or against the active intervention is most likely to hinge on externalities (i.e. antibiotic use and resistance) in the population, rather than purely within trial estimates of costs and quality of life, therefore powering the economic analysis based on trial cost-effectiveness would provide too narrow a focus. The primary comparison will be the cost per antibiotic avoided during the acute episode between those children receiving active eardrops to those receiving no drops (usual care) and to those receiving placebo drops. The incremental NHS treatment costs (i.e. initial ear drops plus antibiotic prescriptions and other health service contacts) during the first 7 days after randomisation will be ascertained from the Symptom and Recovery Questionnaire and Day 8 telephone call and valued using national unit costs.^{54 55} Opportunity costs to parents (i.e. lost work days, out of pocket expenses) and children (school absences) will be measured at the Day 8 telephone call, and valued using human capital and shadow price approaches.

Bootstrapping will be used to calculate confidence intervals around the point estimate of the incremental costeffectiveness ratio and cost-effectiveness acceptability curves. We will investigate the effect of any differences in baseline characteristics and if necessary will use regression techniques to adjust for these. To assess the potential effects of missing data, multiple imputation methods will be utilised in a sensitivity analysis. In the secondary economic analysis we will conduct a cost consequence study tabulating 3 month societal treatment costs (including data from the 3 month questionnaire and GP note review) alongside other important outcomes including 24-36 hour ear pain relief, overall symptom burden, acute illness duration (the end of which will be defined as the last day post randomisation on which parent-reported child ear pain scores zero for two consecutive days without other analgesic medication), CHU-9D utilities (in school aged children, and through multiple imputation to children outside this age range) and OMQ-14 quality of life scores.

Our study will provide decision-makers with an estimate of any incremental costs of the active intervention and any benefits in terms of reduced antibiotic prescriptions, reduced symptoms and improved quality of life. If the active intervention does reduce antibiotic use without a detrimental impact on symptoms, we will discuss the implications for parents and the NHS of making the drops available over the counter (this will be explored through the qualitative interviews). We envisage this to be part of drawing policy implications from our findings, rather than a formal extrapolation model.

A full Health Economics Analysis Plan will be developed and reviewed by the Trial Steering Committee.

Qualitative analysis

Interview transcripts will be checked for accuracy and then imported into NVIVO qualitative data analysis software, to aid management and indexing of data. Analysis will begin shortly after data collection starts, will be ongoing and iterative. Analysis will inform further data collection: for instance, analytic insights from data gathered in earlier interviews will help identify any changes that need to be made to the topic guide during later interviews. Thematic analysis,⁵⁷ utilising a data-driven inductive approach,⁵⁸ will be used to identify and analyse patterns and themes of salience to participants and across the dataset using constant comparison techniques.^{59 60} First, transcripts will be read several times, to gain familiarisation with the data and initial ideas. Transcripts will then be examined line-by-line with inductive codes being assigned to data segments that provide insight to participants' views and understandings. An initial coding frame will be developed and new data compared to previous data, and then to the properties of emerging categories that contain the main themes. The process of constant comparison will allow for the generation of new themes, re-classify themes and incorporate themes within other themes, with the coding frame being modified, if needed, as analysis develops. The data will be scrutinised for negative cases and reasons for the deviance explored by comparison with the whole dataset. Transcripts from the parents' and health care professionals' interviews will be analysed separately, with coding frames being developed for each separate phase. A subset of transcripts will be independently double-coded by other members of the research team and compared: any discrepancies will be discussed and resolved to achieve a coding consensus and to maximise rigour.

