7.7. Use of alternative rescue therapies i.e. oral analgesics

Our PPI group has confirmed that parents will wish to use rescue therapy in the event of ongoing pain. Responsible Clinicians will be asked to provide standardised advice regarding the stepped use of oral analgesics, starting with: (i) paracetamol; (ii) switching to ibuprofen;¹¹ and (iii) using both together or alternating.¹² If the drops provide effective analgesia then it is likely that oral analgesic use will be higher in the placebo group and this could reduce the observed effect of active drops on pain. We will measure use of rescue paracetamol, ibuprofen and other pain-killing therapies (through the Symptom and Recovery Questionnaire) and both adjust for any differences between groups in our multivariable model (if necessary), and investigate the relationship between the contemporaneous use of ear drops and other analgesics (including interactions) on outcomes.

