12. ANALYSIS

12.1. Sample size calculation

Antibiotic consumption (primary outcome)

Current United Kingdom (UK) antibiotic prescribing rates are high for children with AOM, in fact higher than for any other respiratory infection of childhood.⁸ One study showed prescribing rates of 84%,⁹ while another showed three-quarters of UK general practices prescribe antibiotics to at least 80% of children with AOM.⁸ We are not aware of any evidence to inform consumption rate, but our clinical experience and PPI group suggest that the majority of parents will give their child a prescribed antibiotic. Our power calculation therefore (conservatively) assumes a no drop (usual care) arm antibiotic consumption rate of 80 to 90%. While it is agreed that for reducing the development of antimicrobial resistance, antibiotic consumption is more meaningful than prescribing, there is no agreed minimum difference in antibiotic consumption worth detecting. Our work has shown a clear and prolonged link between primary care prescribed antibiotics and antimicrobial resistance lasting over 6 months,¹⁰ and although we did not find evidence to define a clinically important difference in consumption rates, these data¹⁰ suggest that a 20% change in consumption could have important effects on antimicrobial resistance, both in children and in their infectious contacts. Assuming a Type II error rate of 0.1 (90% power) and Type I error rate of 0.05 (alpha) the number of children needed in each group (active eardrops and no drops) ranges from 92 to 119 to demonstrate a 20% fall in antibiotic consumption from 80-90% in the control group to 60-70%. Using the more conservative estimate of 119, and taking into account 20% attrition, this would give a final sample size of 149 per arm.

Pain (secondary outcome)

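### The primary logistic model takes its covariates from observed baseline imbalance and leaves out centre, so the adjusted estimate depends on the data and does not reflect the stratified design

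*Protocol*

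**What the plan says.** **Primary model.** Protocol section 12.5 (Statistical analysis) compares antibiotic use by Day 8 between active drops and no drops by intention to treat. On covariates it says: "Logistic regression will be utilised and the findings adjusted for marked imbalance at baseline". The bracketed illustration is of variables that "differ by more than 0.5 standard deviations for age or univariable significant differences in proportions such as those with bilateral AOM". It opens with *e.g.*, so the list is not closed. No covariate is fixed in advance and centre is not mentioned.

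**Design.** Section 12.3 (Randomisation): "We will stratify by centre so that the distribution of the three arms are fairly equal between Bristol, Cardiff and Southampton".

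**Pain model.** Section 12.5 treats the key secondary outcome differently. It specifies linear regression "adjusting for baseline pain score (collected prior to randomisation) and centre". It then brings the imbalance rule back in a further model: "This will be followed by a linear regression model where all other principles described for the primary analysis above will be applied".

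**Analgesics.** Section 7.7 says that for rescue analgesia the team will "both adjust for any differences between groups in our multivariable model (if necessary"). Section 12.5 twice keeps post-randomisation analgesics out of the main models and assigns them to secondary mediation analyses.

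**The concern.** This is a stated rule, not a gap left for the SAP. An SAP that follows it inherits the problem, and one that departs from it contradicts the protocol.

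In a properly randomised trial, baseline differences between arms are chance. A test of such a difference says nothing about whether the variable predicts the outcome, which is the reason to adjust for it. Choosing covariates this way means that the model behind the primary result is known only after the arms have been compared. Because the list is open, someone must also decide afterwards which variables to examine. Leaving out the stratification factor means that the analysis does not match the randomisation, and the protocol treats centre differently in its two main models.

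At stake are a primary estimate whose definition is not fixed beforehand and some precision given up for nothing. The validity of the test is not at stake.

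**Working it through.** **1. The plan's sample size (section 12.1).** "Assuming a Type II error rate of 0.1 (90% power) and Type I error rate of 0.05 (alpha"), two-sided, pooled-variance formula:

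n = [1.96·√(2p̄(1−p̄)) + 1.2816·√(p₁(1−p₁)+p₂(1−p₂))]² / (p₁−p₂)²

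- 80% v 60%: (1.2702 + 0.8105)²/0.04 = 108.2, so 109; with continuity correction, 119.
- 90% v 70%: (1.1087 + 0.7019)²/0.04 = 82.0, so 82; with continuity correction, 92.
- Attrition: 119/0.8 = 149. The pain outcome sets the final size: 133/0.8 = 167 per arm, and 3 × 167 = 501.

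The stated 92, 119, 149, 167 and 501 all reproduce. The calculation has no covariates. At 133 evaluable per arm, unadjusted power is 94.9% (80 v 60) or 98.6% (90 v 70).

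**2. The age trigger.** Under randomisation the standardised mean difference has SE √(2/n).

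| n per arm | SE | 0.5/SE | P(difference > 0.5 SD) |
|---|---|---|---|
| 167 | 0.109 | 4.57 | 0.000005 |
| 133 | 0.123 | 4.08 | 0.00005 |

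**3. The significance trigger.** Assuming a 5% level and k independent proportions, the chance that at least one enters is 1 − 0.95^k: 14% for k = 3, 23% for k = 5 and 40% for k = 10. The protocol does not give k.

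**4. Why the choice changes the estimate.** An odds ratio changes when a prognostic covariate is added, even with balanced arms. For 80% v 60% the unadjusted OR is (0.6/0.4)/(0.8/0.2) = 0.375. Suppose two equal strata have control rates of 95% and 65% (assumed; mean 80%). An active mean of 60% then needs a within-stratum OR of about 0.293: 19 × 0.293 = 5.57, or 84.8%; 1.857 × 0.293 = 0.544, or 35.2%; mean 60%. So whether the trigger fires decides whether the reported OR estimates 0.375 or 0.29.

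**5. Power and type I error by simulation.** 133 per arm, 3,000 runs per setting, centre balanced. The protocol gives no covariate strength, so OR 1.5 to 3 per SD and a centre log-odds SD of 0 to 0.5 are assumed.

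| Setting | Imbalance rule | Pre-specified covariate + centre | Gain (points) |
|---|---|---|---|
| 80 v 60 | 95.0–95.8% | 95.9–98.2% | 0.5–2.5 |
| 80 v 65 | 78.0–79.2% | 79.8–86.6% | 1–8 |

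Centre alone adds 0 to 0.5 points at 80 v 60 and at most about 2 at 80 v 65. Under the null, also counting runs with a non-prognostic covariate, rejection is 4.0–4.8% for the imbalance rule and 4.6–5.5% for the pre-specified model (Monte Carlo SE about 0.4 points).

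**6. A strong binary predictor, half the children in each level.**

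| Control rates by level (assumed) | Overall | Unadjusted | Always adjusted |
|---|---|---|---|
| 90/70% | 80 v 60 | 95.3% | 96.6% |
| 95/65% | 80 v 60 | 95.2% | 98.2% |
| 97/83% | 90 v 70 | 98.7% | 99.3% |
| 60/10%, OR 0.45 | 35 v 23 | 62% | 72% |
| 70/15%, OR 0.45 | 42.5 v 29 | 61% | 74% |
| 85/30%, OR 0.45 | 57.5 v 44 | 59% | 75% |

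The first three rows use the plan's rates: the gain is about 1 to 3 points, and every unadjusted figure is above 90%. The last three assume lower consumption and a smaller effect: the gain is roughly 10 to 17 points allowing for simulation error, and the imbalance rule recovers almost none of it.

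**The case against.** **The SAP will settle it.** A full SAP is promised, the triggers are only illustrations, and a covariate list is ordinary SAP content. This stands for the exact list. It does not stand for the principle of selecting on observed imbalance, which the protocol fixes and repeats for the further pain model.

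**Nothing is lost at the planned effect.** This largely stands. Type I error is held, unadjusted power exceeds 90%, and the gain is 1 to 3 points. A reader might infer from the low-rate scenarios that the trial is underpowered because of the covariate rule. The documents do not support that: the low power there comes from rates and an effect below those in section 12.1. It remains true that section 12.1 takes its 80–90% largely from prescribing rates and says there is no evidence on consumption.

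**Prescribing strategy.** A reader might also infer that the model omits the strongest predictor, the clinician's choice of no or delayed prescription. No section ranks predictors; the only causal link stated is pain (section 4.3). The strategy is a plausible strong predictor and no more. Nor is it safely a baseline variable as the text stands. Section 9.4 lists planned management, but its statement about timing before randomisation follows the quality-of-life item. Section 9.12 allows CRF entry up to 24 hours after recruitment, by which time the opened pack has shown drops or no drops (section 9.6).

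**Analgesics.** A reader might take section 7.7 to mean that the main pain result will be biased by adjusting for a consequence of treatment. Section 12.5 bars that adjustment from the main models, so the section 7.7 clause is a conflict of wording to reconcile.

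**Conclusion.** The point holds in limited form. Section 12.5 fixes a poor rule: covariates enter the primary model on observed imbalance, through an age trigger that is inert and a significance test that is uninformative about prognosis, from an open list. The primary model also omits centre, although randomisation is stratified by it and the pain model includes it. The adjusted primary estimate is therefore data-dependent and does not reflect the design.

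The practical size is small on the plan's own figures: no type I inflation, no shortfall against 90% power, and about 1 to 3 points of power forgone. The loss reaches roughly 10 to 17 points only if consumption and effect are both lower than planned and a strong predictor is available. The trigger probabilities rest on randomisation alone. All power gains rest on assumed covariate strengths, because the protocol gives none.

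**What to change.** 1. In section 12.5, specify the primary logistic model in advance: treatment, centre and a short named list of baseline covariates, for example age, bilateral AOM and baseline pain.
2. Delete the 0.5 SD and significance triggers, or keep them only as a labelled sensitivity analysis. Make the same change in the further pain model that borrows them.
3. Add planned prescribing strategy (no v delayed) only if it is documented before the Patient Pack is opened. That needs a recording step in sections 9.4 and 9.12, not just new text in section 12.5.
4. Reconcile the adjustment clause in section 7.7 with section 12.5, which keeps post-randomisation analgesics out of the main models.

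Items 1, 2 and 4 are wording changes, to be made before allocation is revealed to the analysts, and do not affect the sample size. Item 3 carries a small procedural cost at sites.
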